## 5. Study Design

### 5.1. Summary of Study Design

Study J2T-DM-KGAD (KGAD) [aka DRM06-AD06] is a randomized, double-blind, placebo-controlled, parallel-group study in adult and adolescent ( $\geq 12$  to  $< 18$  years weighing  $\geq 40$  kg) patients with moderate-to-severe atopic dermatitis (AD). The study is designed to evaluate the safety and efficacy of lebrikizumab when used in combination with topical corticosteroid (TCS) treatment compared with placebo in combination with TCS treatment. Approximately 225 patients will be enrolled into the study. The study has 1 treatment periods (16-week). Patients completing this 16-week study will be offered continued treatment in a separate long-term extension study J2T-DM-KGAA (DRM06-AD07). Patients who early terminate or choose not to enter the long-term extension study will undergo a follow-up visit approximately 12 weeks after the last study drug injection for safety follow-up.

#### 5.1.1. Screening Period

**Screening Period:** Patients will be evaluated for study eligibility before the baseline visit (Day 1). Electronic diary collection will begin at screening.

#### 5.1.2. Baseline and Double-Blinded Treatment Period (Week 0 to Week 16)

At baseline visit (Day 1), patients who meet the study eligibility criteria will be 2:1 randomly assigned to their treatments with stratification based on geographic region (US versus EU versus rest of world), age (adolescent patients 12 to  $< 18$  versus adults  $\geq 18$  years) and disease severity (Investigator Global Assessment [IGA] 3 versus 4). The treatment groups in the Blinded Period are:

- Lebrikizumab 250 mg every 2 weeks (Q2W): 500 mg lebrikizumab administered at Baseline and Week 2 (loading dose; 2 pre-filled syringes with a pre-assembled needle safety device [PFS-NSD]) and 250 mg Q2W through Week 14.
- Placebo: 4 mL (2 PFS-NSD) administered at Baseline and Week 2 and 2 mL Q2W through Week 14.

#### 5.1.3. Safety Follow-Up Visit

Patients who terminate early from the study or do not enroll in the long term extension study, J2T-DM-KGAA (DRM06-AD07), will undergo a follow up visit approximately 12 weeks after the last study drug injection.

Figure KGAD.5.1 illustrates the study design.

**Figure KGAD.5.1. Illustration of study design for Clinical Protocol KGAD.**

## 5.2. Determination of Sample Size

For FDA: Approximately 225 patients will be randomized at a 2:1 ratio to lebrikizumab or placebo (150 patients:75 patients). The assumed IGA score of 0 or 1 at Week 16 response rates are 38% for lebrikizumab 250 mg Q2W and 13% for placebo. The assumption for lebrikizumab is based on the DRM06-AD01 Phase 2b study, the proportion of patients who achieved an IGA score of 0 or 1 at Week 16 using the rescue medication non-response sensitivity analysis, adjusting for the allowed use of TCS/topical calcineurin inhibitors (TCI). The placebo response rates are based on the review of historical TCS clinical studies in AD. This study has power >95% for testing superiority of lebrikizumab to placebo based on a two-sided Fisher's exact test with alpha of 0.05.

For European Medicines Agency (EMA): Approximately 225 patients will be randomized at a 2:1 ratio to lebrikizumab or placebo (150 patients:75 patients). The assumed IGA score of 0 or 1 at Week 16 response rates are 38% for lebrikizumab 250 mg Q2W and 13% for placebo. The assumed Eczema Area and Severity Index (EASI) 75 response rate at Week 16 response rates are 58% for lebrikizumab 250 mg Q2W and 20% for placebo. The assumptions for lebrikizumab are based on the DRM06-AD01 Phase 2b study, the proportion of patients who achieved an IGA score of 0 or 1 and proportion of patients who achieved EASI75 response at Week 16 using the rescue medication non-response sensitivity analysis, adjusting for the allowed use of TCS/TCI. The placebo response rates are based on the review of historical TCS clinical studies in atopic dermatitis. This study has power >95% for testing superiority of lebrikizumab to placebo based on a two-sided Fisher's exact test with alpha of 0.05.

## 5.3. Method of Assignment to Treatment

All patients will be randomly allocated to receive the study treatment using an electronic data capture (EDC) system at the Baseline visit. The allocation to treatment will be prospectively stratified by geographic region (US versus EU versus rest of world), age group (adolescent patients 12 to <18 years versus adults  $\geq 18$  years) and disease severity (IGA 3 versus 4). At the Baseline visit (Day 1), once a patient is considered eligible to participate in the study, demographic and stratification information will be entered into the EDC system to receive a medication number assigning a kit to a patient.

## 6. A Priori Statistical Methods

### 6.1. General Considerations

Statistical analysis of this study will be the responsibility of Eli Lilly and Company (Lilly). The latest version of the Medical Dictionary for Regulatory Activities (MedDRA) will be used.

Analyses and summaries from assessment of endpoints described in the protocol (for example, described in KGAD Protocol Table 1) are planned to be included in a clinical study report (CSR). Analyses and summaries for key safety data are also planned to be included in the CSR. Results from additional efficacy analysis and other safety analyses may also be provided in the CSR as deemed appropriate.

Any change to the data analysis methods described in the protocol will require a protocol amendment ONLY if it changes a principal feature of the protocol. Any other change to the data analysis methods described in the protocol and the justification for making the change will be described in the CSR.

All statistical processing will be performed using SAS® unless otherwise stated. Some of the analyses described in this document will be incorporated into interactive display tools instead of or in addition to static displays. Except where noted, all statistical tests will be two-sided and will be performed at the 0.05 level of significance.

The Schedule of Visits and Procedures outlined in the protocol specifies the allowable windows for assessments. Assessments performed outside these windows will not be excluded from any analysis, unless specified otherwise.

#### 6.1.1. Analysis Populations

Analysis populations are defined in [Table KGAD.6.1](#) along with the analysis they will be used to conduct.

[Table KGAD.6.2](#) describes the treatment groups and the comparisons for each study period and the analysis population.

**Table KGAD.6.1. Analysis Populations**

Population	Description
All Entered Patients	All patients who signed informed consent. Patient flow will be summarized.
ITT Population	All randomized patients, even if the patient does not take the assigned treatment, does not receive the correct treatment, or otherwise does not follow the protocol. Patients will be analyzed according to the treatment to which they were assigned.
Modified ITT (mITT) Population	ITT Population excluding all patients from PPD . Patients will be analyzed according to the treatment to which they were assigned. Unless otherwise specified, efficacy and health outcomes analyses will be conducted on this population.
Safety Population	All randomized patients who received at least 1 dose of study treatment.
Modified Safety Population	Safety Population excluding all patients from PPD . Unless otherwise specified, safety analyses will be conducted on this population.

Abbreviation: ITT = intent-to-treat.

**Table KGAD.6.2. Treatment Groups and Comparisons and Analysis Population**

Study Period	Analysis Population	Treatment Groups	Abbreviation	Inferential Comparisons When Applicable
Treatment Period	mITT; Modified Safety; Safety	Placebo; Lebrikizumab 250 mg Q2W	PBO; LEB250Q2W	LEB250Q2W vs PBO

Abbreviations: mITT = modified intent-to-treat; LEB = lebrikizumab; PBO = placebo; Q2W = every 2 weeks.

### 6.1.2. General Considerations for Analyses

Treatment period starts after the first injection of study treatment at Baseline Visit (Day 1) and ends after patient completed Week 16 visit or the early termination visit (ETV) (between Day 1 and Week 16). For patients who are randomized but not dosed, the Double-Blinded Treatment Period starts on the date of randomization.

Baseline will be defined as the last available value before the first injection for efficacy and health outcome analyses. In most cases, this will be the measure recorded at Baseline Visit (Day 1). If the patient does not take any injection, the last available value on or prior to randomization date will be used. Change from baseline will be calculated as the visit value of interest minus the baseline value.

For Pruritus Numeric Rating Scale (NRS) and Sleep-Loss due to Pruritus collected via eDiary, the baseline period is the 7-day window prior to the first injection. A patient must have responses on at least 4 of 7 days to calculate a baseline weekly mean. If a patient has responses for 3 or fewer days, the baseline mean value will be considered missing. eDiary data for Pruritus NRS and Sleep-loss due to Pruritus are mapped to study visit per [Appendix 1](#).

For the safety analyses, the following baselines will be used. For safety analyses using a baseline period, the baseline period is defined as the time from Screening Visit to the date/time of the first injection in Treatment Period.

- Treatment-emergent adverse events (TEAEs): baseline will be all results recorded during the baseline period.
- Treatment-emergent abnormal laboratory and vital signs results: baseline will be all results recorded during the baseline period.
- Change from baseline to last observation or to each scheduled post baseline visit for laboratory and vital signs results: baseline will be the last scheduled non-missing assessment recorded during the baseline period.

The randomization to treatment groups is stratified by geographical region (US versus EU versus rest of world), age group (adolescent patients 12 to <18 years versus adults  $\geq 18$  years) and baseline disease severity (IGA 3 versus 4) as described in Section 5.3. The countries will be categorized into geographic regions for analysis (Section 6.3). Unless otherwise specified, the statistical analysis models for Treatment Period will adjust for geographic region, age group and baseline disease severity.

For assessments of the primary endpoints and other binary efficacy and health outcomes endpoints, the following will be provided:

- Crude proportions for each treatment group along with the 95% two-sided asymptotic (that is, not continuity corrected) confidence intervals (CIs).
- The estimated common risk difference along with 95% CIs. The common risk difference is the difference in proportions adjusted for the stratification factors as mentioned in Section 6.3. SAS PROC FREQ will be used for the estimates and CIs, where the CIs are calculated by using Mantel-Haenszel-Sato method (Sato 1989).
- Cochran-Mantel-Haenszel (CMH) test will be used to compare the treatment groups while adjusting for the stratification factors. The CMH p-value will be reported, and the CMH adjusted odds ratio along with the 95% two-sided asymptotic (that is, not continuity corrected) CIs.

Treatment comparisons of key continuous efficacy variables and health outcome variables at each postbaseline time point will be made using analysis of covariance (ANCOVA) with the following in the model: treatment group, baseline value, and stratification factors mentioned in Section 6.3. Type III tests for least squares (LS) means will be used for statistical comparison between treatment groups. The LS mean difference, standard error, p-value, and 95% CI, unless otherwise specified, will also be reported.

Treatment comparisons of other continuous efficacy variables and health outcome variables with multiple postbaseline measurements will be made using mixed-model for repeated measures (MMRM). When MMRM is used, the model includes treatment, baseline value, visit, the interaction of the baseline value-by-visit, the interaction of treatment-by-visit, and the stratification factors mentioned in Section 6.3 as fixed factors. The covariance structure to model the within-patient errors will be unstructured. If the unstructured covariance matrix results in a lack of convergence, the heterogeneous Toeplitz covariance structure, followed by the heterogeneous autoregressive covariance structure will be used. The restricted maximum likelihood (REML) will be used. The Kenward-Roger method will be used to estimate the denominator degrees of freedom. Type III tests for the LS means will be used for the statistical comparison; the 95% CI will also be reported.

For variables that are not collected at each postbaseline visit, data may exist at visits where the variable was not scheduled to be collected. In these situations, data from the early discontinuation visit that do not correspond to the planned collection schedule will be excluded from the MMRM analysis (Andersen and Millen 2013). Also for by-visit summaries/displays such as boxplots, the weeks when data was not scheduled to be collected may not be displayed. However, unscheduled assessments within any defined study period will still be used in the shift analyses, and for imputing values for the change from baseline to last observation carried forward (LOCF) endpoint analyses.

The Kaplan-Meier (KM) product limit method may be used to estimate the survival for time to event analyses. The log-rank test stratified by the stratification factors mentioned in Section 6.3 will be reported. A Kaplan-Meier plot of the time to event by treatment group may be provided.

Unless specified otherwise, Fisher's exact test will be used for adverse events (AEs) and other categorical safety measures. Odds ratios will be created with lebrikizumab treatment as the numerator, and placebo as the denominator. Continuous vital sign and laboratory values will be analyzed by an ANCOVA with treatment and baseline value in the model.

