
 
• Proportion of patients with EASI-75, EASI-90 and EASI-50 by visit
 
• Proportion of patients with IGA Score of 0 or 1 and a reduction <math>\geq 2</math> points from Baseline by visit
 
• Percentage change from Baseline in EASI Score by visit
 
• Percentage change from Baseline in Pruritus NRS by visit
 
• Percentage of patients with a Pruritus NRS score of <math>\geq 4</math> points at Baseline who achieve a <math>\geq 4</math>-point reduction from Baseline by visit
 
• Percentage of patients with a Pruritus NRS score of <math>\geq 5</math> points at Baseline who achieve a <math>\geq 4</math>-point reduction from Baseline by visit
 
• Percentage of patients with Pruritus NRS change of <math>\geq 4</math> from Baseline by visit
 
• Change from Baseline in Sleep-Loss score by visit
 
• Percent change from Baseline in Sleep-Loss score by visit
 
• Change from Baseline in DLQI by visit
 
• Change from Baseline in CDLQI by visit
 
• Percentage of patients with a DLQI total score of <math>\geq 4</math>-points at Baseline who achieve <math>\geq 4</math>-point improvement in DLQI from Baseline by visit
 
• Percentage of patients who achieve <math>\geq 4</math>-point improvement in DLQI from baseline to Week 16
 
• Percentage of patients with a Sleep-loss score <math>\geq 2</math> points at Baseline who achieve a <math>\geq 2</math>-point reduction from Baseline by visit
 
• Change from Baseline in EQ-5D by visit
 
• Change from Baseline in POEM by visit
 
• Change from Baseline in PROMIS Anxiety measure by visit
 
• Change from Baseline in PROMIS Depression measure by visit
 
• Change in ACQ-5 score from Baseline to Week 16 in patients who have self-reported comorbid asthma
 
• Percentage of patients with an IGA score of 0 or 1 and a reduction <math>\geq 2</math> points at by visit in adults
 
• Percentage of patients with a Pruritus NRS score of <math>\geq 4</math> points at Baseline who achieve both an IGA score of 0 or 1 and a reduction <math>\geq 2</math> points from Baseline, and a <math>\geq 4</math>-point reduction in Pruritus NRS score from Baseline by visit
 
• Percentage of patients with a Pruritus NRS score of <math>\geq 4</math> points at Baseline who achieve both EASI-75 and a <math>\geq 4</math>-point reduction in Pruritus NRS score from Baseline by visit
 
	

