**Table KGAD.6.9. Description of Efficacy/Health Outcome Analyses**

Measure	Variable	Analysis Method (Section 6.1)	Population (Section 6.1.1)	Comparison/Time Point	Analysis Type
Investigator’s Global Assessment (IGA)	Proportion of patients achieving IGA [0,1] with a $\geq 2$ -point improvement	CMH analysis with MCMC-MI	mITT	Leb 250 mg Q2W vs PBO; Week 16 and all scheduled visits in Treatment Period	Primary analysis: W16; Secondary analysis: other timepoints
		CMH analysis with NRI	mITT	Leb 250 mg Q2W vs PBO; Week 16 and all scheduled visits in Treatment Period	Supplementary analysis
		CMH analysis with tipping point analysis	mITT	Leb 250 mg Q2W vs PBO; Week 16	Sensitivity analysis
	Proportion of patients achieving IGA [0]	CMH analysis with NRI	mITT	Leb 250 mg Q2W vs PBO; Week 16 and all scheduled visits in Treatment Period	Secondary analysis
	Proportion of patients achieving both IGA [0,1] with a $\geq 2$ -point improvement and a $\geq 4$ -point improvement in Pruritus Numeric Rating Scale (NRS)	CMH analysis with MCMC-MI	mITT with Baseline Pruritus NRS score at least 4	Leb 250 mg Q2W vs PBO; Week 16 and all scheduled visits in Treatment Period	Secondary analysis
CMH analysis with NRI		mITT with Baseline Pruritus NRS score at least 4	Leb 250 mg Q2W vs PBO; Week 16 and all scheduled visits in Treatment Period	Secondary analysis	
Eczema Area and Severity Index (EASI)	Change from baseline in EASI score	ANCOVA with MCMC-MI	mITT	Leb 250 mg Q2W vs PBO; Week 16 and all scheduled visits in Treatment Period	Secondary analysis: percent change Week 16
	Percent change from baseline in EASI score	MMRM	mITT	Leb 250 mg Q2W vs PBO; Week 16 and all scheduled visits in Treatment Period	Secondary analysis

Description of Efficacy/Health Outcome Analyses

Measure	Variable	Analysis Method (Section 6.1)	Population (Section 6.1.1)	Comparison/Time Point	Analysis Type
	Proportion of patients achieving EASI-75	CMH analysis with MCMC-MI	mITT	Leb 250 mg Q2W vs PBO; Week 16 and all scheduled visits in Treatment Period	Primary analysis: EASI-75, W16; Secondary analysis: EASI-90, W16; Secondary analysis: other timepoints
	Proportion of patients achieving EASI-90				
	CMH analysis with NRI				
		CMH analysis with tipping point analysis	mITT	Leb 250 mg Q2W vs PBO; Week 16	Sensitivity analysis
	Proportion of patients achieving EASI-50	CMH analysis with MCMC-MI	mITT	Leb 250 mg Q2W vs PBO; Week 16 and all scheduled visits in Induction Period	Secondary analysis

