### **Summarize Unadjusted Response Rate**

The response rates, overall and by treatment arm, and their associated standard errors (SEs) are computed for each imputed data set using PROC FREQ with the *riskdiff* option specified for the appropriate column in the TABLES statement. The response rates and SEs from the resulting output are combined across the 25 imputed data sets using PROC MIANALYZE, separately for each arm and the overall group.

Note that the estimate and 95% confidence interval (CI) bounds output by PROC MIANALYZE are percents (that is, they are in terms of the response rate). To obtain the number of responders, the estimated percent is multiplied by the number of individuals in the analysis population and rounded to the nearest integer.

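### Each arm's response rate gets a Wald-type 95% interval at every visit; if early placebo response to strict endpoints is rare, these descriptive intervals under-cover in a 75-patient arm (minor reporting correction)

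*SAP*

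**What the plan says.** SAP 6.1.2 sets one reporting rule for binary outcomes: "For assessments of the primary endpoints and other binary efficacy and health outcomes endpoints, the following will be provided". The first item is "Crude proportions for each treatment group along with the 95% two-sided asymptotic (that is, not continuity corrected) confidence intervals (CIs". The other items are the stratified common risk difference with a Mantel-Haenszel-Sato interval, the CMH p-value and the adjusted odds ratio.

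Appendix 3 (Summarize Unadjusted Response Rate) says how the arm-level figures are built under multiple imputation: "The response rates and SEs from the resulting output are combined across the 25 imputed data sets using PROC MIANALYZE". The interval bounds are those output by that procedure.

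Table KGAD.6.9 schedules IGA 0/1, IGA 0, EASI-75, EASI-90 and the two pruritus composites at "Week 16 and all scheduled visits in Treatment Period". Table KGAD.4.1 lists, among other efficacy endpoints, "Proportion of patients with EASI-75, EASI-90 and EASI-50 by visit". IGA 0 is analysed with nonresponder imputation (NRI) only. IGA 0/1, EASI-75, EASI-90 and the composites are analysed with both MCMC multiple imputation (MI) and NRI.

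On size, SAP 5.2 says "Approximately 225 patients will be randomized at a 2:1 ratio to lebrikizumab or placebo (150 patients:75 patients". Neither section gives an alternative interval for arms with no or few responders.

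**The concern.** A Wald interval takes its width from the observed proportion. With few responders that width is too small, and with none it is zero. Entry requires IGA of at least 3 (protocol 4.1), so IGA 0/1 response is 0% at baseline by design, and it is assumed to reach only 13% on placebo by Week 16. IGA 0 cannot exceed IGA 0/1, and a composite cannot exceed either of its components within the same subset. Low placebo counts at the first visits are therefore plausible for the strict endpoints.

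What is at stake is the honesty of the by-visit tables and error bars. A 95% interval of 0% to 0% claims certainty from 75 patients, and a negative lower limit is an impossible response rate. Both faults would fall mainly on the smaller control arm.

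**Working it through.** **Inputs.** Planned arms 150 and 75 (SAP 5.2). Week 16 planning rates: IGA 0/1 "response rates are 38% for lebrikizumab 250 mg Q2W and 13% for placebo"; EASI-75 "response rates are 58% for lebrikizumab 250 mg Q2W and 20% for placebo". Early-visit placebo rates are not in the documents, so a range is used.

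**The plan's own figure.** The documents give no coverage figure. Their stated power, above 95% by two-sided Fisher's exact test at 0.05, is reproduced by exact enumeration with 150 and 75 patients: 98.4% for 38% vs 13% and 99.99% for 58% vs 20%.

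**Intervals compared**, with p = x/n and z = 1.96:
- Wald: p ± z·√(p(1−p)/n)
- Wilson: [p + z²/(2n) ± z·√(p(1−p)/n + z²/(4n²))] / (1 + z²/n)

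**Coverage.** For a true rate π, sum the Binomial(75, π) probabilities of every x whose interval contains π. The chance of a zero-width Wald interval from zero responders is (1−π)^75; for example 0.99^75 = 47.1%.

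| True rate | P(0 of 75) | Wald | Wilson |
|---|---|---|---|
| 1% | 47.1% | 52.8% | 96.0% |
| 2% | 22.0% | 77.9% | 93.6% |
| 3% | 10.2% | 89.6% | 97.5% |
| 4% | 4.7% | 80.4% | 97.0% |
| 5% | 2.1% | 89.0% | 94.5% |
| 6% | 1.0% | 93.9% | 95.5% |
| 7% | 0.4% | 89.7% | 96.0% |
| 8% | 0.2% | 93.9% | 95.0% |
| 10% | 0.0% | 94.3% | 95.0% |
| 13% (IGA 0/1, Week 16) | 0.0% | 92.2% | 94.4% |
| 20% (EASI-75, Week 16) | 0.0% | 93.1% | 94.1% |

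Wald coverage saw-tooths because counts are discrete. From 6% to 10% it is about 94% at most of the listed rates, but it dips (89.7% at 7%). Severe failure is confined to about 2% and below.

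**Observed counts, n = 75.**
- 0 responders: Wald 0.0% to 0.0%. Wilson upper limit z²/(n+z²) = 3.84/78.84 = 4.9%.
- 1 responder: p = 1.33%, SE = √(0.01333 × 0.98667/75) = 1.32%, Wald −1.3% to 3.9%; Wilson 0.2% to 7.2%.
- 2 and 3 responders: Wald lower limits −1.0% and −0.4%; Wilson 0.7% and 1.4%.

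**Smaller denominators.** The composites use only patients with baseline Pruritus NRS of at least 4, and the mITT population drops some patients. With an assumed n of 50, Wald coverage is 39.5% at 1%, 63.5% at 2% and 92.0% at 5%.

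**Multiple imputation.** Rubin's total variance is T = W + (1 + 1/25)·B, where W is the mean of p_k(1−p_k)/n and B is the variance of the p_k over the 25 sets. T is zero only if every set has a rate of 0 (or every set 1). Suppose one set has one placebo responder and 24 have none. Then pooled p = (1/75)/25 = 0.053%, W = 7.02×10⁻⁶, B = 7.11×10⁻⁶ and T = 1.44×10⁻⁵. The Wald-type interval then has positive width, but its lower limit is below zero.

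**The case against.** Several points on the other side stand.

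- **The low rates are assumed.** A reader might infer that near-zero early placebo rates are documented. They are not. The control is placebo plus TCS started at Baseline (protocol 6.3), after at least a week without topical anti-inflammatory treatment (protocol 4.2, exclusion 3). In the earlier open-label phase 2 comparison (protocol 1.3.1.2), the TCS group of 27 reached IGA 0/1 in 25.9% and EASI-75 in 37.0%, with no time point given there. Near-zero rates are plausible for IGA 0 or EASI-90 at Week 2, and less so for EASI-75 or EASI-50.
- **No early-onset claim depends on these intervals.** A reader might infer that evidence of early effect is biased towards the drug. The documents do not support that. Every primary and major secondary endpoint in SAP 6.6 is at Week 16, and comparisons at any visit use the CMH test, the stratified risk difference and the odds ratio.
- **Zero observed responders does not by itself collapse an MI interval.** None of the 25 imputed sets may have a responder in that arm.
- **The word asymptotic could include a score interval.** Appendix 3 closes that reading for imputed data. For NRI, Wald is the natural reading of 6.1.2 but not the only possible one.
- **Timing.** SAP Version 4 was written after the primary database lock, so a further change would also come after lock.

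These points limit the importance of the concern. They do not make a 0% to 0% interval, or a negative lower limit, acceptable output.

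**Conclusion.** The point holds as a minor reporting correction. The plan prescribes a Wald-type arm-level interval for imputed data and, on the natural reading, for NRI data, and gives no provision for sparse counts. Given a 75-patient arm and true rates of about 2% or less, coverage falls to 78% or lower. At 3% to 5% it is 80% to 90%, and at the Week 16 planning rates 92% to 93%, which is 1 to 2 points below Wilson. The case most exposed is IGA 0, where NRI is the only method and zero observed responders gives a zero-width interval with certainty.

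The size rests on two assumptions: early-visit placebo rates, which the documents do not give, and 75 evaluable placebo patients. The coverage figures are for fully observed data; MI adds between-imputation variance but keeps the symmetric form. Treatment comparisons, the multiplicity scheme and power are unaffected.

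**What to change.** - **SAP 6.1.2:** name the Wilson score interval for arm-level NRI and observed rates.
- **Appendix 3:** compute a Wilson interval from the pooled proportion p, with effective sample size p(1−p)/T, where T is Rubin's total variance. With no missing data this returns the actual arm size.
- **Fallback:** when the rate is 0 in all 25 sets, or 1 in all 25, use the Wilson interval with the actual arm size.
- **Do not pool on the logit scale:** the logit is undefined for any imputed set with no responders.

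The cost is SAP wording and a small macro change. Intervals at low rates become asymmetric and usually wider. The effective-size rule can also be conservative at the edge. In the example with one responder in one of 25 sets, the effective size is 0.000533 × 0.99947 / 1.44×10⁻⁵ ≈ 37 and the Wilson upper limit is about 9.5%, against 4.9% for the 0/75 fallback. Point estimates, p-values, risk differences and odds ratios do not change. Because the plan was already amended after the primary lock, the change should be recorded as a post-lock reporting change.

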**Major Secondary Endpoints:**

2. [EASI-75 W16] Percentage of patients achieving EASI-75 ( $\geq 75\%$  reduction from Baseline in EASI score) at Week 16.
3. [Pruritus NRS-4 W16] Percentage of patients with a Pruritus NRS of  $\geq 4$ -points at Baseline who achieve a  $\geq 4$ -point reduction from Baseline to Week 16.
4. [EASI-75 & Pruritus NRS-4 W16] Percentage of patients with a Pruritus NRS score of  $\geq 4$  points at Baseline who achieve both EASI-75 and a  $\geq 4$ -point reduction in Pruritus NRS score from Baseline at Week 16
5. [EASI-90 W16] Percentage of patients achieving EASI-90 ( $\geq 90\%$  reduction from Baseline in EASI score) at Week 16.

Figure KGAD.6.1 Describes the gatekeeping testing scheme for US submission.

Abbreviations: EASI = Eczema Area and Severity Index; IGA = Investigator Global Assessment; NRS = Numeric Rating Scale; W = week.

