#### **Major Secondary Endpoints:**

3. [EASI-90 W16] Percentage of patients achieving EASI-90 ( $\geq 90\%$  reduction from Baseline in EASI score) at Week 16.
4. [EASI Percent Change from Baseline W16] Percentage change in EASI score from Baseline to Week 16.

5. [Pruritus NRS-4 W16] Percentage of patients with a Pruritus NRS of  $\geq 4$ -points at Baseline who achieve a  $\geq 4$ -point reduction from Baseline to Week 16.
6. [Pruritus Percent Change from Baseline W16] Percentage change in Pruritus NRS score from Baseline to Week 16.
7. [EASI-75 & Pruritus NRS-4 W16] Percentage of patients with a Pruritus NRS score of  $\geq 4$  points at Baseline who achieve both EASI-75 and a  $\geq 4$ -point reduction in Pruritus NRS score from Baseline at Week 16
8. [DLQI CFB W16] Change from Baseline in DLQI at Week 16.
9. [DLQI W16] Percentage of patients with a Dermatology Life Quality Index (DLQI) total score of  $\geq 4$ -points at Baseline who achieve a  $\geq 4$ -point improvement from Baseline to Week 16.
10. [Sleep loss CFB W16] Change from Baseline in Sleep-loss score at Week 16

Figure KGAD.6.2 describes the gatekeeping testing scheme for EU submission.

Abbreviations: CFB = Change from baseline; DLQI = Dermatology Life Quality Index ; EASI = Eczema Area and Severity Index; IGA = Investigator Global Assessment; NRS = Numeric Rating Scale; PCFB = Percent change from baseline ; W = week.

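### The CMH tests of Pruritus NRS-4, EASI-75 with NRS-4, and DLQI-4 are valid but leave out the baseline score, forgoing power by an amount that depends on inputs the documents do not give

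*SAP*

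**What the plan says.** For binary endpoints SAP 6.1.2 states: "Cochran-Mantel-Haenszel (CMH) test will be used to compare the treatment groups while adjusting for the stratification factors". SAP 6.3 and Appendix 3 name the factors as geographic region, age group and baseline IGA 3 or 4. Protocol 9.1 likewise prescribes CMH for dichotomous variables.

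For key continuous endpoints, the same SAP section uses ANCOVA "with the following in the model: treatment group, baseline value, and stratification factors mentioned in Section 6.3".

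Three major secondary endpoints count a fall of at least 4 points among patients who start at 4 or more:

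- The item beginning "Pruritus NRS-4 W16] Percentage of patients with a Pruritus NRS of" is US item 3 and EU item 5.
- EASI-75 together with NRS-4 is US item 4 and EU item 7.
- The item beginning "DLQI W16] Percentage of patients with a Dermatology Life Quality Index (DLQI) total score of" is EU item 9 and is not in the US family.

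For these three, the baseline score enters the responder definition, the eligibility cut at 4 and the imputation model (SAP 6.4.1). It does not enter the test.

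**The concern.** With an absolute 4-point threshold, baseline is part of how difficult response is. A patient at NRS 4 must reach 0; a patient at 9 need only reach 5. None of the three stratification factors measures itch or DLQI. If response depends on baseline, a test that ignores it leaves explained variation in the noise and does not correct a chance imbalance in starting score between arms. The score is already collected and is already a covariate for the continuous versions of the same scales. At stake is power for alpha-controlled secondary claims for which the documents state no power.

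**Working it through.** **The plan's own figure.** SAP 5.2: "Approximately 225 patients will be randomized at a 2:1 ratio to lebrikizumab or placebo (150 patients:75 patients"; IGA "response rates are 38% for lebrikizumab 250 mg Q2W and 13% for placebo"; EASI-75 "58% for lebrikizumab 250 mg Q2W and 20% for placebo"; two-sided Fisher's exact test at 0.05; "This study has power >95% for testing superiority of lebrikizumab to placebo". For IGA by normal approximation:

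- Pooled rate = (57 + 9.75)/225 = 0.297.
- Null SE = sqrt(0.297 × 0.703 × (1/150 + 1/75)) = 0.0646.
- Alternative SE = sqrt(0.38 × 0.62/150 + 0.13 × 0.87/75) = 0.0555.
- z = (0.25 − 1.96 × 0.0646)/0.0555 = 2.22, so power is 98.7%.

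Exact enumeration for Fisher's test gives 98.4% for IGA 0/1 and 99.99% for EASI-75. The statement is right for those two endpoints and is silent on the three at issue.

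**Sparsity.** 3 regions × 2 age groups × 2 IGA levels = 12 strata. With about 200 patients (assumed) that is 200/12 = 16.7 per stratum, about 5.6 of them on placebo.

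**Simulation.** Everything below is assumed, because the documents give no baseline distribution, response rates or baseline-to-outcome relation for these endpoints.

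- Week 16 score = arm constant + slope × baseline + IGA effect + normal error, floored at 0. Response is a fall of at least 4.
- NRS: baseline mean 7.2, SD 1.8, truncated to 4–10, residual SD 2.2.
- DLQI: mean 14, SD 7, truncated to 4–30, residual SD 6. It has fewer patients because those aged 16 or under complete the CDLQI.
- 2:1 permuted blocks within the 12 strata, complete data, 10,000 trials per case.

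At slope 1 the fall does not depend on baseline. At slope 0.4, placebo NRS-4 response runs 16%, 29% and 45% from the lowest to the highest baseline third.

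Power, %:

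| Endpoint (n; placebo v active) | Slope | Planned CMH | Logistic, strata only | Logistic, strata + baseline | Gain over CMH |
|---|---|---|---|---|---|
| NRS-4 (200; 30 v 50) | 1.0 | 77.6 | 78.8 | 78.7 | 1.1 |
| | 0.8 | 77.4 | 78.6 | 79.2 | 1.8 |
| | 0.6 | 77.5 | 78.8 | 80.6 | 3.1 |
| | 0.4 | 77.4 | 78.6 | 82.3 | 4.9 |
| | 0.2 | 77.2 | 78.3 | 84.3 | 7.1 |
| EASI-75 + NRS-4 (200; 20 v 38) | 0.8 | 76.1 | 77.4 | 77.7 | 1.6 |
| | 0.6 | 75.3 | 76.8 | 77.6 | 2.3 |
| | 0.4 | 74.9 | 76.3 | 78.4 | 3.5 |
| | 0.2 | 75.1 | 76.6 | 79.5 | 4.4 |
| DLQI-4 (160; 55 v 76) | 0.8 | 75.8 | 77.0 | 77.9 | 2.1 |
| | 0.6 | 75.5 | 77.0 | 80.2 | 4.7 |
| | 0.4 | 76.4 | 78.2 | 83.8 | 7.4 |
| | 0.2 | 76.9 | 78.6 | 87.3 | 10.4 |

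The step from CMH to strata-only logistic (1.1 to 1.8 points here) owes nothing to baseline. Baseline's own share is the next step: −0.1 to 6.0 points for NRS-4, 0.3 to 2.9 for the composite and 0.9 to 8.7 for DLQI-4.

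Sensitivity of the total gain:

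- NRS-4 at 170 patients: 2.1 to 7.9 points over slopes 0.8 to 0.2.
- NRS-4 at 30% v 55%, where CMH power is already about 92%: 0.8 to 3.6.
- Further runs under other assumptions, slopes 1 to 0.2: 0.3 to 6.7 for NRS-4 and 0.4 to 11.6 for DLQI-4.
- NRS-4 with the fall proportional to baseline: 63.6% to 67.8%, and 84.0% to 87.7%. With the fall unrelated to baseline: 70.4% to 71.0%, and 83.9% to 84.2%.

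**Baseline as extra CMH strata.** Relative to the planned CMH, a median split changed power by −3.2 to +3.7 points and tertiles by −5.8 to +2.4.

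**Type I error at nominal 5%.** The planned CMH ran at 4.5 to 5.3% in the main set (up to 5.5% in other runs). Logistic with baseline ran at 4.7 to 5.6% for NRS-4, 5.3 to 5.6% for the composite and 5.1 to 6.1% for DLQI-4. Monte Carlo SE is about 0.2 to 0.25 points.

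**The case against.** The planned CMH is valid, follows Protocol 9.1, and pairs naturally with the estimand's difference in response proportions and with the Mantel-Haenszel risk difference. No power target exists for these endpoints. The size of any gain rests wholly on assumed inputs and can be close to nothing. A logistic p-value tests a conditional odds ratio, so it could disagree with a risk difference not adjusted for baseline score. The EU family already contains baseline-adjusted itch and DLQI tests (items 6 and 8). SAP Version 4 was written after primary database lock, when a few study-team statisticians had been unblinded; changing a confirmatory test then is more than an edit.

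Most of this stands. It makes the point one of efficiency, expressed as a range, with a condition on timing. It does not explain why the plan uses baseline for the continuous NRS and DLQI endpoints but not for their responder versions, and the US family has no continuous counterpart.

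A reader might infer that the tests are biased or that their type I error is inflated; the simulations show neither. A reader might also infer that one failure stops everything listed after it. The lists are described as sequential, but the routing of alpha is in Figures KGAD.6.1 and KGAD.6.2, which are not shown, so that cannot be confirmed.

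**Conclusion.** The point holds as a low-severity efficiency improvement, not an error. Moving from the planned CMH to logistic regression with strata plus continuous baseline gains about 0 to 7 points of power for NRS-4 with about 200 patients (7.9 in the steepest case at 170), about 2 to 4 for the composite and about 0 to 12 for DLQI-4. Up to about 2 points of each comes from leaving the sparse CMH. No simulated case lost power with a continuous covariate. The result rests on the assumed baseline distributions, response rates, sample sizes, slopes and complete data.

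It would be tempting to quote a single ceiling for all three endpoints, or to call the gain free of type I cost. Neither is supported. The range differs by endpoint and by a slope the documents do not give, and size ran slightly above nominal for the composite and DLQI-4.

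**What to change.** In SAP 6.1.2 and Table KGAD.6.9, for these three endpoints only, test treatment by logistic regression with treatment, region, age group, baseline IGA and continuous baseline NRS (or DLQI) in each imputed data set, pooled by Rubin's rules. Appendix 3 already pools log odds ratios. From the same model, report a baseline-standardised marginal risk difference beside the Mantel-Haenszel difference, and keep CMH as supportive. Align Protocol 9.1, or record the departure as SAP 6.1 allows. Leave IGA 0/1, EASI-75 and EASI-90 on CMH. Do not add baseline as further CMH strata, which can lose power.

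Confirm size by simulation first, especially for the composite and DLQI-4. The decision must be taken by blinded statisticians before unblinding. Otherwise, because Version 4 follows primary database lock, CMH should remain the confirmatory test and the adjusted model should be supportive only.

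The cost is SAP and protocol wording, one standard model and a size simulation. A residual drawback is that a p-value from a conditional odds ratio and an interval for a risk difference can occasionally disagree near the significance boundary.
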